
We anticipate continuing enrollment and analyses concurrently for the first three years of the study. We will continue enrollment of new participants until month nine of year 4—to ensure that the great majority of participants have completed the six-month study and that all participants will be followed for a minimum of three months post-randomization.

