Implementation Factors: Qualitative Interviews (30 mins) will be conducted by the RA/Tracker with the first 10 patients at each Site assigned to the ID/LAB model at a timepoint during the 12 to 24 week period post-randomization to elicit personal accounts of their experience with the service, its acceptability, and suggestions for improvement. Participants who are unable to complete the interview by the final study timepoint, will be offered the opportunity to complete the interview at a later and more convenient date, if they wish to do so. Providers (the physicians and Nurse Care Managers delivering ID/LAB at each Site) will be interviewed at about 6 months to a year after starting enrollment about feasibility, acceptability, barriers, and facilitators within their practices and suggestions for improvement or facilitation of implementation. An interview guide will be developed during study start-up in consultation with clinical teams, and incorporating standard implementation outcomes (Glasgow et al., 1999). The interviews will be recorded and transcribed. Using Atlas.ti® software and a coding framework developed from the interview guide, the study collaborators at the Columbia Site ([name] and [name]) will systematically code transcripts of the interviews, and these will be discussed at the weekly-convened study team conference call with the MPIs, Site PIs, and local Site Study Coordinators for consensus discussion. These descriptive implementation data will

be used to fine-tune the implementation of the ID/LAB model at the Study Sites, and to inform development of a brief Guideline to support dissemination of the model beyond the study.

Study Timeline

Please refer to the Study Visit Schedule, located after the Table of Contents, for a detailed schematic of all measurables and their timing

Pre Screening

As discussed above (Section 5.0, Inclusion/Exclusion Criteria/Study Populations), the research team will receive referrals for pre-screening through a variety of mechanisms including a daily chart review of the Infectious Disease/Hospitalist patient lists, weekly correspondence with Infectious Disease fellows, and electronic health record inbox messages from ID/hospitalist providers. For those that are pre-screened via chart review, we will obtain a HIPAA waiver for the ability to effectively review information regarding study relevance: documentation of opioid use and an opioid related infection.

Screening

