12.0 Data Management

Power Analysis: Previous studies of buprenorphine initiation in an Emergency Department⁴² and on a medical inpatient service,⁴³ yielded rates of post-discharge buprenorphine maintenance treatment in the 70% range. The Emergency Department study implemented a Screening, Brief Intervention and Referral control condition, similar to the TAU condition planned in the current protocol, which yielded a rate of post-discharge buprenorphine maintenance treatment of 45%. We anticipate that the population recruited for this study will be among the most severely ill patients with OUD, being those requiring hospitalization for infections, and therefore we conservatively assume that the proportion of patients meeting our primary outcome (enrolled in MOUD 12 weeks after hospital discharge) will be 40% in the TAU arm and 60% in ID/LAB arm. We have chosen a sample size of N = 200 total (N = 100 per study arm), in order to ensure sufficient power (power = 80%) with a two-sided level of significance of 5% to detect a difference of at least 19.7% between the TAU and ID/LAB treatment groups (i.e., 40% treatment enrollment in the TAU arm and at least 59.7% treatment enrollment in the ID/LAB arm). This rate difference of 19.7% is equivalent to an odds-ratio of 2.2 and would be clinically meaningful.

Data Analysis Plan:

Primary outcome: The primary outcome will be a binary indicator of whether a patient is enrolled in and receiving effective MOUD (buprenorphine, methadone, or injection naltrexone) at 12 weeks (3 months) after randomization.

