(WHOQOL-Bref); continuous); 2) Opioid craving (continuous); 3) Pain (Modified PEG scores; continuous).

Intent to Treat, Dropouts, and Missing Data: All analyses will be on the Intent-to-treat (ITT) sample, i.e., all randomized subjects (N=200) according to the treatment arm to which they were assigned. For the primary outcome and secondary outcomes related to treatment engagement, any patients lost to follow-up will be assumed not to be enrolled in treatment nor to have completed the antimicrobial course. Loss to follow-up will be minimized through collection of extensive locator information at baseline and proactive outreach, as described above. For the secondary outcomes related to substance use, missing data (patients who cannot be located) will be assumed to be opioid positive (not abstinent), a typical assumption which is reasonable based on the high rate of relapse among patients with OUD who discontinue medication treatment.^{14,44-46} For other secondary outcomes, missing data will be treated as missing at random. Longitudinal mixed effects models do not require complete data to provide estimates of the outcome, and the estimates are considered valid under the assumption that the data are missing at random.⁴⁷ We will additionally perform sensitivity analysis for the secondary outcomes to examine the influence on the outcomes of dropout and missing data by performing several imputation methods, for instance imputing missing weeks as all abstinent or all non-abstinent. Comparison of the inferences from assuming various models for the missingness provides a measure of the validity of the efficacy estimate from the initial model.

Significance Testing and Preliminary Analyses: All tests for main effects will be performed at two-sided significance level of 5%. Before performing specific analyses, we will examine the distributions of outcome measures and covariates and investigate for outliers. The distributions of continuous variables will be checked for normality, and transformed, if necessary. Distribution of demographic and other baseline variables will be examined and described in terms of means, standard deviations, proportions and 95% confidence intervals. Covariates will be examined for association with treatment outcome. Covariates associated with treatment outcome will be adjusted for in models used to test study hypotheses.

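### The qualitative interview can give about 30 ID/LAB participants, and no TAU participants, an extra tracker contact before week 24, where participants who cannot be found count as opioid positive

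*Combined protocol and SAP*

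**What the plan says.** Section 10.0, Implementation Factors, has the RA/Tracker hold 30-minute qualitative interviews "with the first 10 patients at each Site assigned to the ID/LAB model at a timepoint during the 12 to 24 week period" after randomization. The note under the Study Schedule gives the same window. Anyone not interviewed by the last study timepoint may be interviewed later. No interview is planned for TAU patients. The physicians and nurses delivering ID/LAB "will be interviewed at about 6 months to a year after starting enrollment".

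The RA/Tracker also collects and enters the baseline and follow-up assessments and travels to meet patients when needed (Section 10.0, Research Data Management System; Assessment Team and Procedures).

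For the substance-use outcomes, Section 12.0 says that "missing data (patients who cannot be located) will be assumed to be opioid positive (not abstinent". For treatment-engagement outcomes, loss to follow-up counts as not enrolled. Week 24 is an assessment point for several secondary outcomes, including toxicology-confirmed abstinence. The primary outcome is at week 12.

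On the use of the interviews, Section 10.0 says that the results are to "be used to fine-tune the implementation of the ID/LAB model at the Study Sites, and to inform development of a brief Guideline". Section 4.0 says: "We will continue enrollment of new participants until month nine of year 4".

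**The concern.** Elsewhere the plan tries to keep contact similar in the two arms. Section 10.0 has the Nurse Care Manager see TAU participants on much the same schedule as ID/LAB participants. The patient interview departs from this. It is done by the staff member whose job includes finding people for outcome visits, it may fall anywhere between two outcome visits, and it exists in one arm only.

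A contact in that interval can refresh locator details or lead to a booked week-24 visit. Because an unlocated participant is scored as a failure, each abstinent participant found through the interview turns a scored failure into a success without any change in opioid use. The direction favors ID/LAB.

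The secondary matter is what the pooled effect describes. If interview findings alter how ID/LAB is delivered while patients are still being randomized, the single odds ratio averages over delivery before and after the change. The plan has no record of dates from which to describe this.

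**Working it through.** **The plan's own figure.** Section 12.0 claims "sufficient power (power = 80%) with a two-sided level of significance of 5% to detect a difference of at least 19.7" percentage points, that is, "40% treatment enrollment in the TAU arm and at least 59.7% treatment enrollment in the ID/LAB arm". Inputs: n = 100 per arm, p1 = 0.40, p2 = 0.597, mean 0.4985.

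- Power = Φ[(d√n − 1.96·√(2·p̄·q̄)) / √(p1q1 + p2q2)]
- = Φ[(1.970 − 1.386) / 0.693] = Φ(0.84) = 0.800
- Odds ratio = (0.597/0.403)/(0.40/0.60) = 2.22

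Both stated figures reproduce. They concern week 12 and one constant ID/LAB rate, so the week-24 contact does not touch them.

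**Size of the week-24 effect.**

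- Share of ID/LAB interviewed: 10 per site × 3 sites (Section 12.0 counts three) = 30 of 100. For TAU it is 0 of 100. If the sub-site hospitals in Section 7.0 counted as sites, the share would be larger; the text does not settle this.
- Assumed: gain g in week-24 completion among those 30, and abstinence a among those gained. The documents give neither.
- Artificial difference in week-24 abstinence = 0.30 × g × a.

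| Gain g (points) | Arm-level completion gain | a = 30% | a = 50% | a = 70% |
|---|---|---|---|---|
| 5 | 1.5 | 0.45 | 0.75 | 1.05 |
| 10 | 3.0 | 0.9 | 1.5 | 2.1 |
| 20 | 6.0 | 1.8 | 3.0 | 4.2 |
| 30 | 9.0 | 2.7 | 4.5 | 6.3 |

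For scale, the standard error of a difference in proportions with 100 per arm and 50% in each is √(2 × 0.25/100) = 7.1 points. An artificial 1.5 to 3 points is 0.2 to 0.4 of a standard error.

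**Does the timeline allow changes during enrollment?** Assume uniform accrual of 67 per site from month 0 to month 45 (month nine of year 4).

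- Provider interviews at months 6 to 12: share still to be randomized = 1 − 6/45 to 1 − 12/45 = 87% to 73%.
- First 10 ID/LAB patients ≈ first 20 randomized: 20/(67/45) = 13.4 months. Adding 12 to 24 weeks gives months 16.2 to 19.0, which leaves 64% to 58%.
- If enrollment instead opened at month 9 (36 months of accrual), the shares are 83% to 67% and about 62% to 55%.

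Most participants would be randomized after the findings become available under either start date.

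**Could a before/after analysis settle the effect of a change?** With an assumed 40/60 split and rates of 40% and 60%, the variance of the log ratio of odds ratios is 2/(40 × 0.24) + 2/(60 × 0.24) = 0.347, so SE = 0.59. The ratio detectable at 80% power is exp(2.8 × 0.59) = 5.2. It could not.

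**The case against.** The extra contact is possible, not certain. The window includes the scheduled week-12 and week-24 visits, the interview may be held at one of them, and it may also be held after week 24. Active tracking (Section 14.0) is described for participants in general. Someone who cannot be found cannot be interviewed either, so a gain of 10 to 20 points may be generous. All of this stands. It limits the size, but it does not remove the asymmetry, because the plan equally permits an interview midway between the visits.

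Section 12.0 also plans sensitivity analyses that impute missing weeks as all abstinent or all non-abstinent. This stands in part. With half of those gained abstinent, the all-abstinent rule moves the same 1.5 to 3 points the other way, so the pair brackets the problem. It does not remove the cause, and the main analysis keeps the rule that favors ID/LAB.

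On fine-tuning, a reader might infer that the intervention is set to change mid-trial and that the comparison is thereby compromised. The documents do not support that. Change during enrollment is a strong inference from the wording and the timeline, but it is not stated, and fine-tuning may mean small adjustments. Allocation is concurrent, in blocks of 4 within site, so both arms are randomized throughout. Nor is ID/LAB undefined: Sections 3.0 and 10.0 specify the formulation, induction, who injects, and the nurse's role and contact frequency. Some averaging over delivery is normal in a pragmatic trial.

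**Conclusion.** The asymmetry is real, small and avoidable. Under the plan's missing-data rule, an ID/LAB-only interview between weeks 12 and 24 could add about 1.5 to 3 points to the week-24 abstinence difference. That assumes a 10 to 20 point completion gain in 30 participants, half of them abstinent; over the wider grid the range is about 0.5 to 6.3 points. Week-24 treatment-engagement measures would move in the same direction. The week-12 primary outcome is not affected, because the interview window opens only at week 12.

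On fine-tuning, the supported conclusion is that the plan allows changes at the sites, that its timeline makes them possible while 58% to 87% of participants are still to be randomized (uniform accrual from month 0 assumed), and that no log is required. This bears on how the pooled effect is described, not on whether the ITT test is valid. The documents give no rates by period, so no size can be put on it. A reader might also infer that the Guideline will attach the pooled estimate to a revised model; Section 10.0 does not say that the Guideline will quote an estimate.

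**What to change.** 1. In Section 10.0, Implementation Factors, and in the Study Schedule note, state that the patient interview takes place only after that participant's week-24 outcome forms are complete, or at the scheduled week-12 visit after that visit's forms. Neither creates a separate tracker contact in one arm. The plan already accepts late interviews. The cost is later or less flexible interviews, and some participants lost before week 24 will not be interviewed unless they were seen at week 12. No visits or sample are added.
2. If any interviews have already been held between the two visits, report week-24 completion by arm with and without the interviewed participants.
3. State in Section 10.0 whether fine-tuning may occur while a site is randomizing. If it may, log each change by site and date, and describe the pooled effect accordingly. The cost is a short log. If no change during enrollment is intended, one sentence settles the matter.

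A formal before/after comparison is not worth requiring: it could detect only a ratio of odds ratios near 5, and it would be confounded with calendar changes such as the pandemic procedures in Appendix A.

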11.0 Specimen Collection and Banking (if applicable)

Optional buprenorphine blood analyses will be conducted on patients who are randomized to the LA-B study arm. Enrollment in this sub-study will be ongoing until 24 complete sample sets are collected (i.e., one blood sample collection at three timepoints for each of the 24 patients). Recruitment in the sub-study will continue until the 24th sample set is completed. At that time the 24th sample set is completed enrollment in the sub-study will stop. Participants who are mid-participation in the sub-study at the time the 24th set is completed will be allowed to finish sub-study participation, potentially leading to more than 24 total complete sample sets collected for the sub-study. If it is known that a participant will be unable to complete all three sample collections, they will be withdrawn from the sub-study. Pharmacokinetic data exists for Sublocade® from Phase 3 data, however less data exists for patients in this study population (hospitalized; concurrent infection). Patients will be asked to consent to these blood draws as part of the informed-consent process. Timepoints for measurements are as follows:

Blood draw 1: 1 hour prior to initial Sublocade® dose up to 8 hours after.

Blood draw 2: 24-48 hours post the initial Sublocade® dose (up to 7 days post-dose).

Blood draw 3: 28 days (+/- 7 days) post the initial Sublocade® dose. Blood draw 3 must be collected prior to the second Sublocade® dose.

12.0 Data Management

Power Analysis: Previous studies of buprenorphine initiation in an Emergency Department⁴² and on a medical inpatient service,⁴³ yielded rates of post-discharge buprenorphine maintenance treatment in the 70% range. The Emergency Department study implemented a Screening, Brief Intervention and Referral control condition, similar to the TAU condition planned in the current protocol, which yielded a rate of post-discharge buprenorphine maintenance treatment of 45%. We anticipate that the population recruited for this study will be among the most severely ill patients with OUD, being those requiring hospitalization for infections, and therefore we conservatively assume that the proportion of patients meeting our primary outcome (enrolled in MOUD 12 weeks after hospital discharge) will be 40% in the TAU arm and 60% in ID/LAB arm. We have chosen a sample size of N = 200 total (N = 100 per study arm), in order to ensure sufficient power (power = 80%) with a two-sided level of significance of 5% to detect a difference of at least 19.7% between the TAU and ID/LAB treatment groups (i.e., 40% treatment enrollment in the TAU arm and at least 59.7% treatment enrollment in the ID/LAB arm). This rate difference of 19.7% is equivalent to an odds-ratio of 2.2 and would be clinically meaningful.

Data Analysis Plan:

Primary outcome: The primary outcome will be a binary indicator of whether a patient is enrolled in and receiving effective MOUD (buprenorphine, methadone, or injection naltrexone) at 12 weeks (3 months) after randomization.

Secondary outcomes: 1) Days using opioids, and days injecting drugs per 28 days prior to each major assessment point (weeks 4, 8, 12, and 24 post randomization) (longitudinal, continuous); 2) Urine toxicology-confirmed abstinent (urine toxicology negative for illicit opioids, and self-report negative over past 7 (at week 1) or 30 days (weeks 4, 8, 12, 24) (longitudinal, binary); 3) Completion of the prescribed course of antimicrobial therapy (binary), Re-hospitalization for infection by week 12 (binary); 4) Days using other drugs/alcohol per 28 days prior to each assessment (longitudinal, continuous); 5) Urine toxicology positive for non-opioid drugs (longitudinal, binary); 6) Social functioning and quality of life (WHOQOL-Bref) at 12 and 24 weeks after randomization (longitudinal, continuous); 7) Modified PEG Pain Scale at each assessment (Longitudinal, continuous) 8) HIV risk behaviors—days in past 28 days of vaginal or anal sex without a condom at weeks 4, 8, 12, 24 (longitudinal, continuous); 8) Any needle sharing in past 28 days (longitudinal, binary); 9) Treatment satisfaction (via the TSR)¹² at 12 and 24 weeks (longitudinal, continuous); 10) Discharge “against medical advice” (binary); 11) Cure of index infection (binary); 12) HCV cure or link to treatment (binary); 13) HIV Viral suppression (Viral Load < 200 copies), if HIV positive (binary); 14) overall hospitalization by week 12; 15) ED visits by week 12; 16) Serious adverse events (SAFETEE and non-fatal and fatal overdose) (binary).

Additional variables: *Covariates, primary and secondary analyses: Stratification factors:* Site (3 sites: YNHH; Columbia/Penn State Hershey; South Carolina/Greenville) will be included as a fixed effect in all analyses. *Covariates:* In general, the baseline score for each outcome measure (where applicable) will be included as a covariate in outcome analyses. *Moderators:* A range of baseline moderator variables will be explored including 1) Demographic characteristics (gender, age, ethnicity, living situation (domiciled vs homeless); 2) Modified Pain PEG scores at baseline (continuous) 3) Evidence of fentanyl use at admission (urine toxicology, self-report) (binary); 4) Other substance use at baseline (any cannabis, any stimulant, any heavy drinking days; binary); 5) Probable major depression at baseline (binary based on PHQ score); 5) Type of infection (endocarditis/ osteomyelitis/bacteremia/ cellulitis/ etc.). *Mediators:* 1) Social functioning

(WHOQOL-Bref); continuous); 2) Opioid craving (continuous); 3) Pain (Modified PEG scores; continuous).

Intent to Treat, Dropouts, and Missing Data: All analyses will be on the Intent-to-treat (ITT) sample, i.e., all randomized subjects (N=200) according to the treatment arm to which they were assigned. For the primary outcome and secondary outcomes related to treatment engagement, any patients lost to follow-up will be assumed not to be enrolled in treatment nor to have completed the antimicrobial course. Loss to follow-up will be minimized through collection of extensive locator information at baseline and proactive outreach, as described above. For the secondary outcomes related to substance use, missing data (patients who cannot be located) will be assumed to be opioid positive (not abstinent), a typical assumption which is reasonable based on the high rate of relapse among patients with OUD who discontinue medication treatment.^{14,44-46} For other secondary outcomes, missing data will be treated as missing at random. Longitudinal mixed effects models do not require complete data to provide estimates of the outcome, and the estimates are considered valid under the assumption that the data are missing at random.⁴⁷ We will additionally perform sensitivity analysis for the secondary outcomes to examine the influence on the outcomes of dropout and missing data by performing several imputation methods, for instance imputing missing weeks as all abstinent or all non-abstinent. Comparison of the inferences from assuming various models for the missingness provides a measure of the validity of the efficacy estimate from the initial model.

Significance Testing and Preliminary Analyses: All tests for main effects will be performed at two-sided significance level of 5%. Before performing specific analyses, we will examine the distributions of outcome measures and covariates and investigate for outliers. The distributions of continuous variables will be checked for normality, and transformed, if necessary. Distribution of demographic and other baseline variables will be examined and described in terms of means, standard deviations, proportions and 95% confidence intervals. Covariates will be examined for association with treatment outcome. Covariates associated with treatment outcome will be adjusted for in models used to test study hypotheses.

Primary outcome Statistical Model: *Hypothesis:* Assignment to the ID/LAB arm (OUD managed directly by the ID or hospitalist team with long acting injection buprenorphine) will promote greater enrollment in effective medication treatment for OUD (MOUD) at 12 weeks after randomization, compared to TAU. The effect of randomization to the ID/LAB arm compared to the TAU arm will be estimated using logistic regression with the binary outcome of enrollment (yes/no) modeled as a function of treatment condition (ID/LAB vs TAU), with Site as a fixed effect, and covariates/moderators as listed above under 'Additional Variables'. The odds ratio of the treatment term and its confidence limits will estimate the treatment effect. The raw retention rates in each treatment group and rate differences will be computed for descriptive purposes.

Power Analysis: Previous studies of buprenorphine initiation in an Emergency Department⁴² and on a medical inpatient service,⁴³ yielded rates of post-discharge buprenorphine maintenance treatment in the 70% range. The Emergency Department study implemented a Screening, Brief Intervention and Referral control condition, similar to the TAU condition planned in the current protocol, which yielded a rate of post-discharge buprenorphine maintenance treatment of 45%. We anticipate that the population recruited for this study will be among the most severely ill patients with OUD, being those requiring hospitalization for infections, and therefore we conservatively assume that the proportion of patients meeting our primary outcome (enrolled in MAT for OUD 12 weeks after hospital discharge) will be 40% in the TAU arm and 60% in ID/LAB arm. We have chosen a sample size of N = 200 total (N = 100 per study arm), in order to ensure sufficient power (power = 80%) with a two-sided level of significance of 5% to detect a difference of at least 19.7% between the TAU and ID/LAB treatment groups (i.e., 40% treatment enrollment in the TAU arm and at least 59.7% treatment enrollment in the ID/LAB arm). This rate difference of 19.7% is equivalent to an odds-ratio of 2.2 and would be clinically meaningful.

Secondary outcomes: Statistical Models: For each of the secondary outcomes (see above) the effect of randomization to the ID/LAB arm compared to the TAU arm will be estimated with a model of the same general form as for the primary outcome (independent variables: treatment assignment (ID/LAB vs TAU), Site as a fixed effect, and baseline score as covariate where relevant) using logistic regression models (for binary outcomes), generalized linear model (for continuous outcomes), or longitudinal generalized mixed effects model (for longitudinal outcomes) with appropriate link functions (e.g. logit for binary outcomes). Longitudinal outcomes analyzed using a mixed effects models will utilize a generalized estimating equation with an autoregressive correlation structure (AR(1)) to account for within subject correlation over time, as well a random intercept accounting for between subject variability. In addition to site, covariates that are found to be related to the outcomes will be added to the models to improve the power for detecting significant differences.

Moderation and Mediation: Moderation Statistical Models: The effect of randomization to the ID/LAB vs TAU arms will be estimated for subpopulations based on the demographic and baseline characteristics selected as moderators (see above). We will estimate the moderation effect on primary outcome using a similar model to Aim 1 primary outcome with the inclusion of moderator by treatment interaction: $Y_i = \beta_0 + \beta_1 Trx_i + \beta_2 M_i + \beta_3 Trx_i M_i + \beta_4 C_i + s_i$ where M_i is the moderator status for i^{th} subject and Trx_i is subject's treatment assignment. Regardless of the significance of the interaction term, we will use the model to estimate the 95% confidence interval of the treatment effect for each level or category of the moderator variable, or the treatment effect at selected values of the moderator variable, if continuous. The moderator analyses are exploratory and hypothesis generating, but significant moderator effects can be useful in planning future efforts at implementation of medication treatment for opioid use disorder in medical settings by identifying subgroups that may particularly benefit. Identifying subgroups where there is less benefit may suggest future modifications to the implementation strategy to achieve better effect in those subgroups.

Mediation Statistical Models: The effect of randomization to the ID/LAB vs TAU arms will be estimated when accounting for potential mediators (see above). In particular, we are interested in testing whether an impact of treatment on the primary outcome (enrollment in effective medication treatment at 12 weeks after randomization) is mediated by social functioning, craving for opioids, pain, or mental health symptoms. We will simultaneously estimate both the total effect of treatment assignment on primary outcome and the indirect of treatment assignment on primary outcome mediated through the intended target mediators using structural equation modeling (SEM) in software MPlus.⁴⁸ The indirect effect is estimated by the product of the effect of treatment assignment on the mediator and the effect of the mediator on the primary outcome while adjusting for treatment assignment. SEM will provide an estimate of the indirect effect of each mediator as well as its bootstrapped 95% confidence interval. These mediational analyses can be of heuristic value in suggesting aspects of the ID/LAB implementation strategy that might need strengthening in future research or implementation efforts.

Confidentiality of Data:

The data system will be unitary, hosted on secure servers at Columbia. All sites will access the same system. The system incorporates role-based security, so users only have access to data appropriate to their role, e.g. coordinators for a particular site only have access to data from their site. The system is certified by CUMC IT as secure for the storage of confidential data for research.

The screener will consist of inclusion/exclusion criteria questions only, and an ID number that is separate from their study ID number (if enrolled) will be used.

To ensure protection of confidentiality, assessment/questionnaire data will be entered into the study database with no personal identifiers and source documents will only identify participants by study ID number. Personal identifying information (including locator information) will be kept on paper in locked files at each site. Access to computers used for data entry, data management, and analysis will be password protected and limited to study investigators. All data that includes PHI will only be

stored on the secure servers at Columbia mentioned above, no PHI will be stored on tablets or computers.

Access to this data will be restricted to specific study staff. This information will be collected from each participant at baseline and at follow-up visits only if contact information changes. Contact information will include the participant's name, phone number, address, email address, aliases (if used), and alternative contacts and their contact information. Contact information, such as telephone number is important, as it will be used to remind participants of follow-up visits or to contact a participant if they are late or do not show up to a follow-up visit. Alternative contacts will only be contacted if we cannot get in contact with the participant.

All information will be stored in password-protected tablets or computers with double-password protection for opening specified files, computers have been encrypted in accordance to HIPAA guidelines. All research data not entered into the system created by Columbia will be stored in the double-locked research offices at each study site. Client level data will be stored with research study number and without any unique identifiers. All identifiers that link study number to study subject will be housed in PGP encrypted, password-protected computers available only to the Project Coordinator, Data Manager, co-Principal Investigators, and Statistician. All computers used for study purposes have been encrypted to meet all HIPAA requirements.

Effective October 1, 2017 Certificates of Confidentiality (CoCs) will be issued automatically for any NIH-funded project using identifiable, sensitive information that was on-going on/after December 13, 2016. The CoC will be issued as a term and condition of this award. There will be no physical certificate issued.

Data Monitoring and Quality Control:

Monitoring for the study is provided by Columbia University, including regular data monitoring at the study sites.

Ongoing data and safety monitoring will be conducted weekly during research team meetings attended by the study site PI with the study site team, as well as weekly multi-site conference calls with all of the study sites, PIs, other research team members, and a representative from YCCI and the Data Management groups.

A Quality Assurance Monitor will ensure site readiness via a site initiation checklist and will travel to the sites to perform a complete review of the first 3-5 randomized participant records. The monitor will return to each study site biannually to review 10% of participants' study records as well the site regulatory binder. Every six months, the PIs, the study site teams, and the QA monitor will review the number of participants enrolled, the number who completed the protocol, the number who dropped out of the protocol prior to completion (and reason why), any adverse events, procedures for assuring participant privacy and confidentiality, and the quality and integrity of the data collected. Corrective action will be taken if needed. Investigators will also coordinate monitoring required by the sIRB or any other reporting entity.

No data will reside at MUSC.

13.0 Provisions to Monitor the Data to Ensure the Safety of Subjects (if applicable)

The DSMP is attached to the IRB application.

